4.5 Statistics

Statistical analysis will be performed to analyse the patient recruitments in terms of baseline clinical characteristics. Survival analysis will be used to demonstrate ulcer healing. Biological assays will be analysed using univariate statistical analysis. Metabonomic assay data will be mathematically modelled and analysed using multivariate statistical models.

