1.1 Objectives

We seek to further examine the biology of chronic venous ulceration. Our rationale for this study is:

1. Can we effectively predict from biological markers in whom standard therapy will not culminate in wound healing?
2. Can potential therapeutic targets be identified?
3. What changes occur in the biological profile of a chronic venous ulcer over various points in time?

Our belief is that the potential benefits of this study to wider healthcare community may be in effectively stratifying patients with chronic venous ulceration by risk of treatment failure. This may allow resources to be concentrated on high risk patients.

In addition, identifying therapeutic targets may in the future reduce the proportion of patients in whom standard treatment fails or ulcers recur.

Study of the same patients over time will help us understand the process of healing in chronic venous ulceration and determine the differences in patients who ultimately heal versus those who do not.

2. Eligibility and Inclusion

- Forty patients to be recruited from Vascular Surgery Clinics at Imperial College NHS Trust, and Cambridge University Hospitals NHS Foundation Trust.
- Male or female over the age of 18 years
- Chronic venous ulceration – Defined as wound of greater than four weeks in duration between the foot and the ankle with an Ankle Brachial Pressure Index greater than 0.85.
- Ulceration present for at least four weeks.
- Colour venous duplex evidence of chronic venous insufficiency showing either reflux or obstruction.

3. Exclusion Criteria

- Acute infection in the studied lower limb within the last four weeks
- History of malignancy in the lower limb to be studied
- History of connective tissue disease

- Patients on medications that can cause immunosuppression – Corticosteroids, chemotherapy or radiotherapy for cancer and recombinant immunological medications.

4. Study Design and Methodology

Forty patients who fulfil the criteria for the study will be recruited from Vascular Surgery clinics in hospitals under the auspices of Imperial NHS Trust in London and Cambridge University Hospitals NHS Foundation Trust in Cambridge.

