4.1.2 Subsequent Assessments

- Reassessments of the patient will take place at weeks 1, 2, 4, 8, 12 and 20.
- These will involve reviewing any significant changes in health.
- The ulcer area will be measured using digital planimetry to chart progress of healing.
- Compression bandaging will be continued as per the requirements of the patient.
- Wound fluid, urine and special blood tests will be repeated as described above.

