4.2.1.1 Urine

1. Mid stream urine sample
2. Transfer to 50ml Falcon tube
3. Aliquot 10 x 1ml samples into 2ml Eppendorf
4. Transported to South Kensington Campus on dry ice
5. Freeze at -80 degrees Celsius for storage

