4.2.1.3 Leg Ulcer Fluid

a. Occlusive Dressing Technique (6)

1. Ulcerated area covered in Tegaderm dressing
2. 90 minutes with the leg dependent in a seated position
3. Fluid aspirated with hypodermic 21g needle and syringe
4. Fluid transferred into 10ml 15ml Conical Dome Top Polypropylene Falcon tube and kept on dry ice
5. Collected fluid kept on ice and centrifuged within 30 minutes at 13,000g
6. Supernatant filtered using methylcellulose filter (8)
7. Transfer 0.4ml into 1.5ml Eppendorfs
8. Transport to South Kensington Campus on dry ice
9. Flash frozen and stored at -80 degrees Celsius

b. Filter Disc Technique (7)

1. Preprepared 1cm² absorptive filters from Whatman 54 paper, sterilised in ethanol and oven dried at 60 degrees Celsius. Preweighed in sterile 2ml tubes.

2. Sterile Tegapore mesh placed cut into 4cm² segments and placed onto ulcer. Ten discs placed on top of mesh.
3. After 90 minutes, disc removed from mesh and placed back into tube.
4. Transferred to South Kensington Campus on dry ice
5. Putative Imperial method – Analyse filter discs directly after separation into aqueous and organic extracts
6. Aqueous extract – mass spectrometry and NMR
7. Organic extract – Mass spec ± examination for eicosanoids / inflammatory molecules

Tarloton method

1. Filter discs reweighed to determine quantity of fluid absorbed and placed into extraction buffer.
2. Four hours of agitated extraction and fluid removed for freezing and stored at -80 degrees.

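### Marker analyses have no site term and assay runs have no stated layout, so between-patient comparisons of healed and unhealed ulcers are unprotected if both marker levels and healing differ by site

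*Combined protocol and SAP*

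**What the plan says.** **Sites.** Section 2 gives the source of patients as "Forty patients to be recruited from Vascular Surgery Clinics at Imperial College NHS Trust, and Cambridge University Hospitals NHS Foundation Trust". Section 4 repeats this as "hospitals under the auspices of Imperial NHS Trust in London and Cambridge University Hospitals NHS Foundation Trust in Cambridge". Neither section gives a split by site. Section 4.1.2 leaves bandaging to individual need: "Compression bandaging will be continued as per the requirements of the patient".

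**Handling before the central laboratory (Section 4.2).**
- Occlusive-dressing fluid: "Collected fluid kept on ice and centrifuged within 30 minutes at 13,000g". It is then filtered and aliquoted, and only after that comes "Transport to South Kensington Campus on dry ice".
- Urine: aliquoted, then "Transported to South Kensington Campus on dry ice", with the -80 degree freeze listed last.
- Blood: clotted, spun, aliquoted and frozen. No transport step and no limit from spin to freezer are given.
- Filter discs: sent to South Kensington on dry ice before extraction, so they are extracted centrally.

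Section 4.4.2 stores all samples at -80 degrees in one place before analysis. The label it describes carries the patient number and a specimen-type suffix.

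**Analysis.** Section 4.5 is the only statistics text. For the assays it says "Biological assays will be analysed using univariate statistical analysis"; for metabonomics it names multivariate models without defining them. No section gives a site term, stratification by site, an allocation of samples to runs, a run order or a recorded processing time.

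**The concern.** The first objective in Section 1.1 is to predict from biological markers who will not heal on standard therapy. That compares different patients, so anything that moves both the marker and the chance of healing can create an association.

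Site could do both. Occlusive-dressing fluid has to be spun soon after collection and before transport, so the operator and centrifuge probably differ between London and Cambridge. Urine aliquoting and serum preparation are, by implication, local too. Case-mix and bandaging practice may differ as well, and healing with them.

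If both differences exist, an unadjusted comparison attributes part of the site effect to healing. Markers sensitive to handling would shift together, which a multivariate model could pick up as a pattern. Cross-validation within the pooled sample would not expose it, because training and test sets share the same confounding. Assay run raises the same question if runs happen to follow site or outcome.

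**Working it through.** The plan states no healing rate, SD, alpha or site split, so there is no figure of its own to reproduce. The following is an illustration.

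**From the protocol:** 40 patients, two trusts.

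**Assumed:** 20 patients per site; healing probabilities pA and pB; a marker with SD 1 within site and a shift of s SD at site B; no true marker–healing association; two-sided 5% test.

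**Step 1. Spurious difference.** The share of site B patients is pB/(pA + pB) among the healed and (1 − pB)/(2 − pA − pB) among the unhealed. The expected difference is s times the gap between these shares.
- 60% v 60%: 0.5 − 0.5 = 0.
- 70% v 50%: 0.50/1.20 − 0.50/0.80 = 0.417 − 0.625, size 0.21 SD per 1 SD of shift.
- 75% v 45%: 0.45/1.20 − 0.55/0.80 = 0.375 − 0.688, size 0.31 SD.
- 80% v 40%: 0.40/1.20 − 0.60/0.80 = 0.333 − 0.750, size 0.42 SD.

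**Step 2. False-positive rate.** In each case about 24 patients heal and 16 do not. Take 70% v 50% with s = 1. The variance within outcome groups is 1 + [24(0.417 × 0.583) + 16(0.625 × 0.375)]/40 = 1.24. The standard error is √[1.24 × (1/24 + 1/16)] = 0.359. The ratio k is 0.208/0.359 = 0.58. The rejection rate is approximately Φ(−1.96 + 0.58) + Φ(−1.96 − 0.58) = 0.084 + 0.006 = 0.09.

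Simulation of the t-test, and of a linear model of marker on healing plus site, gave:

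| Healing by site | Shift | Unadjusted | With site term |
|---|---|---|---|
| 60% v 60% | 0.5 or 1 SD | about 5% | about 5% |
| 70% v 50% | 0.5 SD | 6% | about 5% |
| 70% v 50% | 1 SD | 9% | about 5% |
| 75% v 45% | 0.5 SD | 8% | about 5% |
| 75% v 45% | 1 SD | 14% | about 5% |

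A more extreme 80% v 40% gave 9% (0.5 SD) and 21% (1 SD) unadjusted, again about 5% with site in the model. A 28/12 split gave similar or slightly lower unadjusted rates.

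**Step 3. Price of the site term.** With equal sites, the correlation of healing with site is φ = (pA − pB) × 0.25/√[p(1 − p) × 0.25], where p is mean healing. The variance inflation is 1/(1 − φ²).
- 70% v 50%: φ = 0.05/0.245 = 0.204, inflation 1.04.
- 80% v 40%: φ = 0.10/0.245 = 0.408, inflation 1.20.

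**Step 4. Within-patient change.** If a patient's value at every visit is the true level plus the same site constant, the constant drops out on subtraction. The figures above therefore do not apply to change from baseline.

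Nothing here quantifies assay run, because the allocation of samples to runs is not stated.

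**The case against.** A reader might infer that site handling will generate false biomarkers throughout this study. The documents do not support that, for these reasons.

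- **Both conditions are assumed.** No healing rate or marker level by site is given. With equal healing there is no inflation, and with a 0.5 SD shift the rate is only 6–8% in the two main scenarios. The 14% needs a 30-point healing gap and a full 1 SD shift.
- **Transport is not shown to be harmful.** Urine, ulcer fluid and discs travel on dry ice, and no distance or transit time is stated. What remains is that no time limit is set and freezing is listed after transport.
- **Not every specimen is processed on site.** Discs are extracted centrally and urine is not spun. One written procedure fixes spin speeds and aliquot volumes, and sets a 30-minute limit for ulcer fluid.
- **Much of the planned work is within-patient.** The third objective, the profile changes in Section 4.3.4 and the paired exudate specimens in Section 4.3.2 concern change or pairs, where a constant shift cancels.
- **Silence is not exclusion.** Univariate analysis does not rule out a covariate, and central storage is compatible with balanced batches.

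All of this stands, and it limits the point to between-patient comparisons under stated conditions. It does not remove it: the shared procedure reduces site differences without excluding them, site is known for every patient, and the plan commits neither to using it nor to any run layout.

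**Conclusion.** The omission is real and worth correcting; its consequence is conditional. If a marker shifts by site and healing also differs by site, unadjusted between-patient comparisons, chiefly baseline prediction under the first objective, are biased. The false-positive rate per marker is then roughly 6–14% instead of 5% in the main scenarios. These figures rest on an assumed 20/20 split, assumed healing rates and assumed shifts of 0.5 to 1 SD; none comes from the protocol. The documents do not establish that such differences exist, that transport causes them, or that assay run is tied to outcome. This is a sensible, cheap safeguard for a small biomarker cohort, not evidence that its results will be wrong.

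**What to change.** **Section 4.5.** Include site as a single covariate in every between-patient model relating a marker to healing. Adjust the metabonomic data for site before multivariate modelling. Report the unadjusted results as a sensitivity analysis. Any comparison of marker direction site by site should be descriptive only, since 40 patients are too few for it to serve as a test.

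**Section 4.3.** Assay all samples of one patient and specimen type in the same batch, mix sites and healing outcomes across batches, and randomise run order. Record collection-to-freezing time for each sample, because it cannot be reliably recovered later.

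**Cost.** The changes need wording in two sections and one time field on the sample form. The site term uses one degree of freedom and loses some precision if healing differs strongly by site (variance inflation about 1.04 at 70% v 50% and 1.20 at 80% v 40%). Assays have to be batched rather than run as samples arrive, which the planned -80 degree storage already allows.

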4.6 Summary of Study Patient Procedures

First Meeting	Introductions, discussion and consent
---------------	---------------------------------------

Initial Assessment – Week 0	Preliminary evaluation – Interview about medical problems, physical examination. Blood, urine and ulcer fluid sampling. Wound dressing.
Week 1,2, 4, 8 and 12	Clinical review Blood, urine and wound ulcer fluid sampling
Week 20	Clinical review Blood, urine and wound ulcer fluid sampling If wound has not healed, apply Urgostart® dressing to wound dressing. If wound has healed – end of study.
Week 21, 22, 23 and 25	Clinical review Blood, urine and wound ulcer fluid sampling Continue dressing with Urgostart®
Week 28	Clinical review Blood, urine and wound ulcer fluid sampling Completion of Urgostart® dressing End of study

5. Adverse Events

5.1 Definitions

Adverse Event (AE): any untoward medical occurrence in a patient or clinical study subject.

Serious Adverse Event (SAE): any untoward and unexpected medical occurrence or effect that:

Results in death

Is life-threatening – refers to an event in which the subject was at risk of death at the time of the event; it does not refer to an event which hypothetically might have caused death if it were more severe

- Requires hospitalisation, or prolongation of existing inpatients' hospitalisation
- Results in persistent or significant disability or incapacity
- Is a congenital anomaly or birth defect

Medical judgement should be exercised in deciding whether an AE is serious in other situations. Important AEs that are not immediately life-threatening or do not result in death or hospitalisation but may jeopardise the subject or may require intervention to prevent one of the other outcomes listed in the definition above, should also be considered serious.

5.2 Reporting Procedures

All adverse events should be reported. Depending on the nature of the event the reporting procedures below should be followed. Any questions concerning adverse event reporting should be directed to the Chief Investigator in the first instance.

5.2.1 Non Serious Adverse Events

All such events, whether expected or not, should be recorded.

5.2.2 Serious Adverse Events

An SAE form should be completed and faxed to the Chief Investigator within 24 hours. However, hospitalisations for elective treatment of a pre-existing condition do not need reporting as SAEs.

All SAEs should be reported to the <name of REC> where in the opinion of the Chief Investigator, the event was:

- 'related', ie resulted from the administration of any of the research procedures; and

- 'unexpected', ie an event that is not listed in the protocol as an expected occurrence

Reports of related and unexpected SAEs should be submitted within 15 days of the Chief Investigator becoming aware of the event, using the NRES SAE form for non-IMP studies. The Chief Investigator must also notify the Sponsor of all SAEs.

Local investigators should report any SAEs as required by their Local Research Ethics Committee, Sponsor and/or Research & Development Office.

6. Regulatory Issues

6.1 Ethical Approval

The Chief Investigator has obtained approval from the xxx Research Ethics Committee. The study must be submitted for Site Specific Assessment (SSA) at each participating NHS Trust. The Chief Investigator will require a copy of the Trust R&D approval letter before accepting participants into the study. The study will be conducted in accordance with the recommendations for physicians involved in research on human subjects adopted by the 18th World Medical Assembly, Helsinki 1964 and later revisions.

6.2 Consent

Consent to enter the study must be sought from each participant only after a full explanation has been given, an information leaflet offered and time allowed for consideration. Signed participant consent should be obtained. The right of the participant to refuse to participate without giving reasons must be respected. After the participant has entered the study the clinician remains free to give alternative treatment to that specified in the protocol at any stage if he/she feels it is in the participant's best interest, but the reasons for doing so should be recorded. In these cases the participants remain within the study for the purposes of follow-up and data analysis. All participants are free to withdraw at any time from the protocol treatment without giving reasons and without prejudicing further treatment.

6.3 Confidentiality

The Chief Investigator will preserve the confidentiality of participants taking part in the study and is registered under the Data Protection Act.

6.4 Indemnity

Imperial College London holds negligent harm and non-negligent harm insurance policies which apply to this study.

6.5 Sponsor

Imperial College London will act as the main Sponsor for this study. Delegated responsibilities will be assigned to the NHS trusts taking part in this study.

6.6 Funding

Laboratoires Urgo are funding this study with an unrestricted academic grant. No specific payments are being made to participants or investigators.

